4.3 JUSTIFICATION FOR INTERVENTION

The intervention is delivered via text messaging as it is an mHealth intervention that targets behavior improvement when participants are on their own. Participants will receive 4-7 messages from the Companion in intervals of 1-4 hours each day. This limited interval will retain the novelty of the communication and thus interest of the participant in engaging in the study while yielding evaluable data.

4.4 END-OF-STUDY DEFINITION

A participant is considered to have completed the study if he or she has completed the baseline assessment and the 4-month follow-up assessment.

5 STUDY POPULATION

5.1 INCLUSION CRITERIA

1. Provision of signed and dated informed consent form
2. Age >60 y
3. Have a body mass index greater than 25 kg/m²
4. No conditions preventing participation in physical activity lasting 10 to 30 min
5. Have a smart phone

5.2 EXCLUSION CRITERIA

1. Engage in structured physical activity for more than 2 days/week lasting 30 min/session-
2. Regularly use any assistive device for walking.
3. Likely to alter medications pertaining to cardiovascular or metabolic health

5.3 LIFESTYLE CONSIDERATIONS

NA

5.4 SCREEN FAILURES

Screen failures are defined as participants who consent to participate in this study but are not subsequently assigned to the study intervention or entered in the study. Individuals who do not meet the criteria for participation in this trial (screen failure) because of meeting/not meeting one or more exclusion/inclusion criteria, respectively will not be enrolled in the study.

5.5 STRATEGIES FOR RECRUITMENT AND RETENTION

Anticipated number of people to be screened =56; Women and Minorities= at least 50 and 20% respectively; Anticipated number of people to be enrolled =46; Women and Minorities= at least 50 and 20% respectively;

Participation in this study will be sought using flyers (see attached flyer) and email (see attached recruitment email template) to identify interested individuals. We will identify potentially eligible Northeastern employees from University department's online staff directories and obtain individual email addresses from employee directories to contact individual's directly in seeking participation in our study using the aforementioned recruitment email and flyer. Recruitment materials (email and flyer) will include the self-inclusion criteria. Should the conditions not apply to individuals who are contacted, he or she may exclude himself or herself without the need to reveal his or her reasons to the researchers. Recruitment emails will be sent a second time a week later if there is no response on the initial invite. People who meet the self-inclusion criteria and express interest in further information will be asked to set up a time to meet briefly at their Northeastern office/home/virtually with the researchers.

This strategy is appropriate because Northeastern University has over 2000 employees engaged in seated work and will yield the necessary sample size for the study. Additionally, Northeastern University is located in close proximity to several other academic institutions such as the Massachusetts College of Arts, Wentworth Institute of Technology, the New England Conservatory of Music, and Harvard School of Public Health and its Medical School. We will direct recruiting efforts at these institutions as well, which are all less than $\frac{1}{4}$ mile from NU's campus. Additionally, we will reach out to senior centers in Boston and surrounding areas and other resources including social media and listservs that are publicly available.

The targeted distribution of the subjects' racial and ethnic makeup is anticipated to be successful given the demographic distribution in the city of Boston based on estimates obtained from United States Census bureau. According to these data, the distribution of minorities in the general population in Massachusetts is 47.4%, Hispanic or Latino of any race is 19.7%, Black or African American alone is 25.3%, American Indian or Alaska native is 0.3%, Asian alone is 9.6%, and those identifying as being of

two or more races is 5.1%. White adults are the majority at 52.6%. The proportion of women in the city of Boston is 51.9%.

Participants may receive up to \$120 in remuneration, consisting of \$40 for completing 3 measurements either at the Human Performance and Exercise Science Lab or in their place of residence. Payment will be provided after completion of the study, either after the month-6 follow up follow-up or at an earlier point should the participant drop out of the study prior to month 6 follow up, consistent with the measurement completion criteria. The incentive is appropriate and will not be viewed as coercive.

6 STUDY INTERVENTION(S) OR EXPERIMENTAL MANIPULATION(S)

6.1 STUDY INTERVENTION(S) OR EXPERIMENTAL MANIPULATION(S) ADMINISTRATION

6.1.1 STUDY INTERVENTION OR EXPERIMENTAL MANIPULATION DESCRIPTION

The Companion: Companion is based on Self Determination Theory (SDT) and the application of Motivational Interviewing (MI) to creatively use information on behaviors, attitudes, and environmental contexts to create user-Companion interactions that are tailored to participant needs. SDT addresses cognitive and affective factors in human motivation and posits three innate psychological needs that form the basis for optimal self-motivation: competence, relatedness, and autonomy.³⁰ MI is a client-centered counseling method to explore and resolve uncertainty towards changing behavior and to enhance intrinsic motivation to effect change.³¹ SDT and MI are successfully combined to improve physical activity³² because of a common underlying assumption that people have a tendency for personal growth toward psychological integration.^{33,34}

Next, we describe Companion's technological components, their integration, and integrated function: (1) Continuously worn wireless ActiGraph® wrist sensor capture raw motion data. (2) These data are transmitted hourly to a backend. (3) Motion data are processed immediately at the backend using validated machine learning algorithms to characterize data as physical activity (e.g. walking or other) or sedentary. (4) Processed data are visualized by a health coach using a backend interface that temporally displays estimated behavior types. (5) Research assistants will enquire about major automatically detected behaviors (e.g. movement >10 min; sitting >20 min) to determine context (e.g. walk during lunch; in a weekly meeting) using CS-EMA. (6) They can also choose to determine behavior context of any other automatically detected behavior. (7) These automated and manual records will incrementally yield a reliable visual model of major habitual daily behaviors at the backend. Such information will be richer than what was previously available to an interventionist. (8) Based on the model, coaches will use the CS-EMA two-way communication app to intervene and promote prescription component delivery at opportune times (i.e., near-real-time) to help develop routines.

Supervised Exercise Program: For the first 16 weeks, all participants will engage in ~45 to 60 min of aerobic, strength, flexibility and balance training, twice/week.^{29,35} Participants will either visit Northeastern's Exercise Science Lab for supervised personal training or engage virtually over Zoom during the training session. The lead trainers will be an exercise physiologist or a trained graduate student. After the session, the trainer and participant will outline goals and prescription plan for the days prior the next training session and those to be performed by the participant on their own. The plan

will be based on guidelines from the American College of Sports Medicine.^{36,37} Supervised training sessions for the two groups will be scheduled on different days and allocation of participants to a trainer will be at random.

Treatment Group: This group will receive the Companion. Communication during weeks 1 to 4, will focus on gathering information on the participant's motivations, preferences, habits, contexts, and usual behavior patterns to build a typical behavior model for the participant. We expect a decreasing level of change in behavior models that are built using information accrued incrementally over these 4 weeks.²³ Companion will monitor ongoing and recent behavior, communicate with the participant (if necessary) to deliver contextually salient intervention strategies. Additionally, there will be a fixed Companion-initiated communication in the early evening (~4 to 6 pm) to discuss the achievement of that day's goals and prescribe strategies to achieve pending goals.

The nature of the first communication the next morning will be based on participant performance during all waking hours of the preceding day- e.g., encouraging, problem-solving. This is possible because the participant will be instructed to continuously wear the wrist device, which stores motion data in its internal memory. These data will be downloaded to Companion and analyzed.

Regular interaction will enable a corresponding incremental personalization of communication based on knowledge of each participant's communication style and personality. Similarly, such frequent interaction will also enable an incremental knowledge of the participant's changing physical ability and activity preferences, which will facilitate a corresponding increase in personalizing activity prescription.

Control Group: This group will not receive the Companion, which will be the only difference with the treatment group. I.e., the control group will receive standard treatment– the supervised training program and an exercise prescription for those days when they are on their own. This will be done on the two days when control group participants meet face-to-face with the trainer for supervised training.

Primary Outcomes: Total duration and number of bouts of: (i) light and moderate-to-vigorous physical activity and (ii) sedentary behavior measured over a period of one week using accelerometry.^{38,39} Week-long measures will be made at baseline, and weeks 16 and 24.

Exploratory Outcomes: Cardiometabolic health: Plasma glucose, HbA1C, insulin, and lipids. Body composition: lean and fat mass. Physical function. Muscular and aerobic fitness. Cognition.⁴² Perceptions of competence related to health behaviors. Autonomy support (from companion). Autonomous motivation (for physical activity). Relatedness (to the Companion). General satisfaction.

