1 PROTOCOL SUMMARY

1.1 SYNOPSIS

Title:	An Integrated Two-Way Communication and Near-Real-Time Sensing System to Detect and Modify Daily Inactivity among Adults Over Age 60
Grant Number:	5P30AG048785-07
Study Description:	The objective is to test if Companion, an Integrated Two-Way Communication and Near-Real-Time Sensing System, improves and sustains overall daily free-living activity and sedentary behavior in adults over 60 y. The central hypothesis is that Companion will improve overall daily free-living activity and sedentary behavior in adults >60 y and thereby improve their health.
Objectives*:	
Primary Objective: Determine if Companion improves free-living activity and sedentary behavior and sustains this change in adults >60y. In this RCT (n=46), both treatment and control groups will engage in a 16-week supervised exercise program and then be followed-up after 24 weeks.^{1,2} Companion will be deployed in the treatment group (n=23) only. Primary outcomes are daily total and bouts of physical activity and sedentary time.
 
Exploratory Objective: Explore if supplementing supervised exercise with Companion further improves and sustains cardiometabolic health, body composition, cognition, and psychosocial outcomes.

Endpoints*:	
Primary Endpoint: Physical activity and sedentary time: Daily total and bouts
 
Exploratory Endpoints: Anthropometrics; Plasma glucose; HbA1C; Insulin; Lipids; Lean and fat mass; Physical function; Muscular and aerobic fitness; Cognition; perceptions of competence related to health behavior; Autonomy support (from companion); Autonomous motivation (for physical activity); Relatedness (to the Companion); General satisfaction.

Study Population:	N= 46, gender- NA, age >60 y, demographic group- older adults; general health status- healthy; geographic location- Boston and surrounding neighborhoods.
Phase* or Stage:	1A
Description of Sites/Facilities Enrolling Participants:	The Human Performance and Exercise Science (HPES) Laboratory is located in the Behrakis Health Science Center at Northeastern University, which will be the sole site for the study. Participants who do not prefer to have their measurements conducted at their residence will come to the lab to have measurements completed. The study is not intended to include sites outside of the United States.

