3 OBJECTIVES AND ENDPOINTS

OBJECTIVES	ENDPOINTS	JUSTIFICATION FOR ENDPOINTS
Primary		
Determine if Companion improves free-living activity and sedentary behavior and	Daily total and bouts of physical	These physical behaviors are directly impacted by motivation communication

OBJECTIVES	ENDPOINTS	JUSTIFICATION FOR ENDPOINTS
sustains this change in adults >60y.	activity and sedentary time.	aimed at promoting positive behavior change.
Tertiary/Exploratory		
(1) Explore if supplementing supervised exercise with Companion further improves and sustains cardiometabolic health, body composition, physical function, muscular and aerobic fitness, and cognition. (2) Examine factors that mediate and moderate change in physical activity and sedentary behavior.	Cardiometabolic health (Plasma glucose, HbA1C, insulin, and lipids; lean and fat mass; Physical function; Cognition; Perceptions of competence related to health behaviors; Autonomy support (from companion); Autonomous motivation (for physical activity); Relatedness (to the Companion); General satisfaction.	These outcomes may be impacted by change in behavior and communication with Companion

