8 STUDY ASSESSMENTS AND PROCEDURES

8.1 ENDPOINT AND OTHER NON-SAFETY ASSESSMENTS

Table 1. Measures in Laboratory or Home

Measure	Measurement 1: Baseline (1-2 h)	Measurement 2: Follow-up 1 (4 months) (1-2 h)	Measurement 3: End of study (6 months) (1-2 h)
Heart rate and blood pressure	✓	✓	✓
Anthropometrics (Height, weight, waist, and hip circumference)	✓	✓	✓
Body composition (Bioelectrical impedance)	✓	✓	✓
Fasting blood glucose, and lipid profile	✓	✓	✓
Cognitive tests	✓	✓	✓
Physical function tasks	✓	✓	✓
Muscular and aerobic fitness	✓	✓	✓
Other			✓

The following tests and procedures will be conducted in the numbered order. All measurements will be made in a secure location to ensure privacy.

1. **Resting heart rate and blood pressure:** Heart rate and blood pressure will be measured using an automatically inflatable blood pressure arm cuff and monitor. These measures will be conducted in triplicate after a rest of 5 minutes between each measure.
2. **Anthropometrics:** Height and weight will be measured using a stadiometer and a standard digital weight scale, respectively, and circumferences will be measured by a trained research staff member using a measuring tape (in triplicate).
3. **Body composition:** Whole body percent fat and lean mass will be measured using Bioelectrical Impedance (BIA) and will be conducted by trained research staff. During the test, the participant will step bare feet on an electronic scale and hold handheld conduction electrodes. A weak electric current will flow through the body and the voltage is measured in order to calculate impedance of the body and thereby, the % of body fat and lean mass. The test will be completed within 30 s. The participant will not feel anything, and this test is similar to stepping on a weighing scale.
4. **Blood glucose and lipid profiles:** We will measure this using finger-stick blood analyses with a CardioChek Plus device (PTS Diagnostics). The CardioChek Plus is a certified fast, accurate and efficient portable analyzer capable of obtaining a full lipid profile and glucose readings in 90 seconds from a finger stick strip blood sample (15 – 40 micro Liters). The participant's blood will not be stored, as the finger stick analyses are immediate, and the measuring strips are discarded appropriately after the test.

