9.2 SAMPLE SIZE DETERMINATION

Sample size is based on change in HbA1C after 16 weeks of training in adults >60 y (n=22). We used a health outcome variable to compute sample size to examine the translational effect of behavior change due to Companion on the health of adults >60 y. In our data, partial η^2 (effect size) for the interaction effect between group and time (pre – 16 week) equaled 0.5 corresponding to a medium effect size. With alpha of .01, power of 0.85, two groups, 3 repeated assessments, and an estimated inter-correlation between assessments of 0.5, the required sample is 39; we will recruit 46 participants. Hypothesis testing for all outcomes will entail an intent-to-treat two-tailed design with a type I error of 0.05.

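### HbA1c and insulin are listed as exploratory endpoints, and HbA1c is the basis of the sample size, but the assessment section describes no measurement of either.

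*Combined protocol and SAP*

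**What the plan says.** Three places name the two analytes as exploratory endpoints. The synopsis (1.1) has "Anthropometrics; Plasma glucose; HbA1C; Insulin; Lipids; Lean and fat mass". The objectives table (section 3) has "Cardiometabolic health (Plasma glucose, HbA1C, insulin, and lipids". Section 6.1.1, under Exploratory Outcomes, has "Cardiometabolic health: Plasma glucose, HbA1C, insulin, and lipids".

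Section 9.2 gives HbA1c a second role: "Sample size is based on change in HbA1C after 16 weeks of training in adults >60 y (n=22". It explains that a health variable was chosen so that the trial could examine how behaviour change carries over into health. It describes an effect size that "equaled 0.5 corresponding to a medium effect size" and then sets the design: "With alpha of .01, power of 0.85, two groups, 3 repeated assessments", with a correlation of 0.5 between assessments. The required number is 39 and the recruitment target is 46.

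The procedures are in section 8.1. The single blood row in Table 1 is "Fasting blood glucose, and lipid profile", ticked at baseline, month 4 and month 6. Item 4 assigns it to one portable finger-stick analyser, described as "capable of obtaining a full lipid profile and glucose readings in 90 seconds". The same item says that the blood is not kept and the strips are discarded. Section 10.1.4, on stored specimens, is marked not applicable.

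**The concern.** An endpoint needs a procedure that produces it. Here the endpoint lists and the assessment section disagree. A site that follows 8.1 exactly would reach the end of the study with nothing to analyse for two listed outcomes, and with no stored sample from which to recover them.

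HbA1c matters more than an ordinary exploratory endpoint because it is the only variable for which the plan gives a power calculation. If it is not measured, the figure of 0.85 describes a test that will not be carried out, and the planning effect cannot be compared with the trial's own data. Section 10.1.11 commits the trial to registration and to submission of results. Listed outcomes without data would then have to be explained, and a reader could not easily tell a drafting slip from selective reporting.

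**Working it through.** **Step 1. Look for a procedure that yields HbA1c or insulin.**

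| Place | Content | HbA1c or insulin? |
|---|---|---|
| 1.3 Schedule of activities | One generic row for outcome evaluation | Not specified |
| 8.1 Table 1, blood row | Fasting glucose, lipid profile | No |
| 8.1 item 4 | One finger-stick device, stated to give lipids and glucose | No |
| 8.1 Table 1, other rows | Heart rate and blood pressure, anthropometrics, body composition, cognition, function, fitness, counselling and interview | No |
| 8.1 Table 2 | Questionnaires, diet, activity monitors | No |
| 8.2 Safety assessments | Refers to the same finger-stick | No |
| 10.1.4 Stored specimens | Not applicable | No later assay possible |

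Table 1 and item 4 are legible and agree with each other, so damage in text extraction does not explain the gap.

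**Step 2. Reproduce the sample size in 9.2, to see what the 0.85 refers to.**

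Inputs from 9.2: alpha 0.01, power 0.85, 2 groups, m = 3 assessments, rho = 0.5, effect 0.5. The method is noncentral-F power for a two-group repeated-measures ANOVA.

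- Between-group test, with 0.5 entered as Cohen's f: lambda = f² N m / [1 + (m − 1) rho] = 0.25 × 39 × 3 / 2 = 14.625, with 1 and 37 df. Power is 0.859 at N = 39 and 0.847 at N = 38, so the smallest adequate N is 39. This matches the plan.
- Group-by-time interaction, as 9.2 labels it, with partial eta-squared 0.5: f² = 0.5 / (1 − 0.5) = 1, and lambda = f² N m / (1 − rho). The smallest adequate N is 6.
- Interaction with f = 0.5: N = 13.
- Interaction with a conventional medium f = 0.25: N = 44, with power 0.79 at N = 39.

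So 39 is recoverable, but only as a between-group test with f = 0.5 and not as the text labels it. That mismatch is a separate matter and the present point does not depend on it. What matters here is that under every reading the input is an effect on HbA1c.

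No dropout rate is stated. Going from 39 to 46 implies 1 − 39/46 = 15.2%, and 39 / 0.85 = 45.9, which rounds up to 46.

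**Step 3. Can the power be restated for a measured outcome?**

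Not from these documents. They give no standard deviation for physical activity or sedentary time. The nearest figure is the reduction in sitting of about 2.1 h per day in the feasibility work (section 2.2, n = 6), with no measure of spread. No corrected N therefore follows from this point.

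**The case against.** The strongest case on the other side is that this is an omission in an exploratory corner of the plan and that little should be built on it. Several parts of that case stand.

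- A reader might infer that the trial cannot observe any effect on health. The documents do not support that. Blood pressure, anthropometrics, body composition, fasting glucose, lipids, cognition, physical function and fitness are scheduled at all three visits. Only the HbA1c and insulin parts are missing.
- A reader might infer that the primary analysis is damaged. It is not. The primary outcomes come from accelerometry and their measurement is described. A trial may also be sized on earlier data for a variable it does not collect, and this does not invalidate the primary test.
- A reader might infer that 46 is too few. Nothing here shows that. The documents leave the power for the primary outcomes unknown, neither adequate nor inadequate.
- A reader might assume that the endpoint lists are wrong and 8.1 is right. The documents do not settle this. Three sections name the analytes and 9.2 relies on one of them, so the omission could equally lie in 8.1.
- A reader might count 46 × 3 = 138 lost values per analyte. That assumes full attendance and adds nothing to a yes-or-no omission.
- A reader might want plasma glucose relabelled because the test is a finger-stick. The documents do not say how the device expresses glucose, so that change is not supported.

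It can also be said that 8.1 never states that the finger-stick is the only blood test, and that the consent form, which is not available here, may describe more. This limits the claim to the plan as written. It does not remove the contradiction, because 8.1 is where the measurements are set out and it provides for neither analyte.

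**Conclusion.** The point holds as an internal contradiction. Sections 1.1, 3 and 6.1.1 list HbA1c and insulin, and 9.2 rests on HbA1c, while 8.1 and Table 1 provide only fasting glucose and lipids, with no blood stored. If the plan is followed as written, two exploratory endpoints will have no data at any visit, and the only stated power, 0.85, belongs to an outcome the trial does not measure.

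The reach is limited. Both endpoints are exploratory and are treated in 9.4.9 as hypothesis-generating. The primary outcomes and the remaining health outcomes are unaffected. The conclusion assumes that no assay is specified in material outside the documents, such as the consent form. If one is, 8.1 still needs to say so.

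**What to change.** Reconcile the passages before analysis, by one of two routes.

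1. **Remove.** Delete HbA1c and insulin from 1.1, 3 and 6.1.1. In 9.2, state that the HbA1c calculation is a planning figure from earlier data and gives no power for any outcome measured in this trial, including the primary ones. This costs only wording. The downside is the loss of two exploratory endpoints.
2. **Keep.** If the sponsor intends to measure them, add the HbA1c and insulin assays to 8.1 and Table 1, with their visits. This is an extra procedure for participants and staff, and visits already completed without it cannot be recovered because no blood is stored.

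Neither route requires a new sample size. If the sponsor also wants a power statement for a primary activity or sedentary outcome, that is a new calculation. It needs an explicitly assumed standard deviation, with power shown over a range of values, because the documents supply none.
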